6.1.5 Dose Adjustments/Modifications/Delays/Infusion-Related Reaction Management

➤ Daratumumab (IV)

Infusion reactions may lead to the interruption of daratumumab administration. Pre-infusion medications should be administered prior to treatment to reduce the risk of IRRs (see [Section 7.3.1](#)).

Following dilution, daratumumab infusion should be administered IV at the appropriate initial infusion rate, as presented in the table below. Incremental escalation of the infusion rate should be considered only if the previous infusion of daratumumab was well tolerated.

Table 6.2: Infusion rates for daratumumab intravenous

	Dilution volume	Initial infusion rate (first hour)	Increments of infusion rate	Maximum infusion rate
First infusion	1,000 mL	50 mL/hour	50 mL/hour every hour	200 mL/hour
Second infusion ^a	500 mL	50 mL/hour	50 mL/hour every hour	200 mL/hour
Subsequent infusions ^b	500 mL	100 mL/hour	50 mL/hour every hour	200 mL/hour

^a If the subject's first infusion of daratumumab is well tolerated (defined as an absence of $>$ Grade 1 infusion-related reactions during the first 3 hours), the second infusion will be administered as indicated in the table above. If the previous infusion rate is not well tolerated, instructions for the first infusion volume and rate will be used for the second infusion.

^b If the subject's first 2 infusions of daratumumab are well tolerated (defined as an absence of $>$ Grade 1 infusion-related reactions during a final infusion rate of ≥ 100 mL/hour), subsequent infusions will be administered as indicated in the table above. If the previous infusion rate is not well tolerated, instructions for the second infusion rate will be followed.

➤ Infusion-Related Reaction Management for Dara IV

Subjects should be observed carefully during daratumumab infusions. Trained study staff at the clinic should be prepared to intervene in case of an infusion reaction, and resources necessary for resuscitation must be available. Attention to staffing should be considered when multiple subjects will be dosed at the same time. For infusion-related reactions of any grade/severity, immediately interrupt the daratumumab infusion and manage symptoms. Management of infusion reactions may further require reduction in the rate of infusion, or treatment discontinuation of daratumumab.

- Grade 1-2 (mild to moderate): Once reaction symptoms resolve, resume the infusion at no more than half the rate at which the reaction occurred. If the subject does not experience any further reaction symptoms, infusion rate escalation may resume at increments and intervals as appropriate as outlined in *Table 6.2*.
- Grade 3 (severe): Once reaction symptoms resolve, consider restarting the infusion at no more than half the rate at which the reaction occurred. If the subject does not experience additional symptoms, resume infusion rate escalation at increments and intervals as outlined in *Table 6.2*. Repeat the procedure above in the event of recurrence of Grade 3 symptoms. Permanently discontinue daratumumab upon the third occurrence of a Grade 3 or greater infusion-related reaction.
- Grade 4 (life threatening): Permanently discontinue daratumumab treatment.

➤ Daratumumab (SC)

Dara-SC will be administered by SC injection at a fixed dose of 1800 mg. Doses will be administered by manual push over 3-5 minutes in the abdominal SC tissue in left/right locations, alternating between individual doses. The volume of the SC solution will be 15 mL for the 1800 mg dose. Refer to the Daratumumab SC Pharmacy Manual for additional guidance on the administration of Dara-SC. All subjects will be observed for at least 6 hours after the end of the SC injection during Cycle 1 Day 1 and, if deemed necessary by the investigator, after consecutive injections.

➤ Local Injection-Site Reactions

In Study MMY1004 Part 1, SC administration of Dara MD in abdominal SC tissue was associated with local injection-site reactions such as induration and erythema in some subjects. The reactions usually resolved within 60 minutes. Injection-site reactions should be managed per institutional standards.

➤ Infusion-Related Reaction Management for Dara SC

Subjects should be observed carefully during study drug administrations. Trained study staff at the clinic should be prepared to intervene in case of any IRRs, and resources necessary for resuscitation (eg, agents such as epinephrine and aerosolized bronchodilator, also medical equipment such as oxygen tanks, tracheostomy equipment, and a defibrillator) must be available at the bedside.

If an IRR develops, then daratumumab administration should be temporarily interrupted. Subjects who experience AEs during daratumumab administration must be treated for their symptoms. Subjects should be treated with acetaminophen, antihistamine, or corticosteroids, as needed. Intravenous saline may be indicated. For bronchospasm, urticaria, or dyspnea, subjects may require antihistamines, oxygen, corticosteroids, or bronchodilators. For hypotension, subjects may require vasopressors. In the event of a life-threatening IRR (which may include pulmonary or cardiac events) or anaphylactic reaction, daratumumab should be discontinued and no additional daratumumab should be administered to the subject.

Infusion-related Reactions of Grade 1 or Grade 2 for Dara SC

If the investigator assesses a Grade 1-2 IRR AE to be related to administration of study drug, then the daratumumab administration should be paused. When the subject's condition is stable, daratumumab administration may be restarted at the investigator's discretion.

If the subject experiences a Grade 2 or higher event of laryngeal edema, or a Grade 2 or higher event of bronchospasm that does not respond to systemic therapy and does not resolve within 6 hours from onset, then the subject must be withdrawn from daratumumab treatment.

Infusion-related Reactions of Grade 3 or Higher for Dara SC

For IRR AEs (other than laryngeal edema or bronchospasm) that are Grade 3, the daratumumab administration must be stopped and the subject must be observed carefully until resolution of the AE or until the intensity of the event decreases to Grade 1, at which point the daratumumab administration may be restarted at the investigator's discretion. If the intensity of the AE returns to Grade 3 after restart of the daratumumab administration, then the subject must be withdrawn from daratumumab treatment.

For IRR adverse events that are Grade 4, the daratumumab administration must be stopped and the subject withdrawn from daratumumab treatment.

Recurrent Infusion-related Reactions for Dara SC

If a Grade 3 IRR (or Grade 2 or higher event of laryngeal edema, or a Grade 2 or higher event of bronchospasm) recurs during or within 24 hours after a subsequent daratumumab administration, the daratumumab treatment must be discontinued.

➤ Daratumumab Dose Delays and Modification

Dose modification of Dara IV or Dara SC (increase or decrease) is not permitted. Dose delay is the primary method for managing daratumumab-related toxicities. On the first day of each new treatment cycle and before each dose of study drug, the subject will be evaluated by the treating physician for possible toxicities that may have occurred after the previous dose(s). Toxicities are to be assessed according to National Cancer Institute (NCI)-CTCAE, Version 4.03. Cycle delays will be based on the toxicity experienced during the previous cycle of therapy or newly encountered on Day 1 of a cycle.

The study treatment must be withheld if any of the following criteria are met, to allow for recovery from toxicity, regardless of relationship to study drug:

- Grade 4 hematologic toxicity, except for Grade 4 lymphopenia
- Grade 3 or higher thrombocytopenia
- Febrile neutropenia
- Neutropenia with infection, of any grade
- Grade 3 or higher non-hematologic toxicities with the following exceptions:
 - Grade 3 nausea that responds to antiemetic treatment within 7 days
 - Grade 3 vomiting that responds to antiemetic treatment within 7 days
 - Grade 3 diarrhea that responds to antidiarrheal treatment within 7 days
 - Grade 3 fatigue that was present at baseline or that lasts for <7 days after the last administration of daratumumab
 - Grade 3 asthenia that was present at baseline or that lasts for <7 days after the last administration of daratumumab

Study treatment should be resumed when the toxicity has resolved to \leq Grade 2. If study drug administration does not commence within the prespecified window of the scheduled administration date (*Table 6.3*), then the dose will be considered a missed dose. Administration may resume at the next planned dosing date. A missed dose will not be made up.

Table 6.3: Daratumumab administration schedule

Cycles	Frequency	Dose Withheld	Dosing Restart
1 and 2	Weekly (q1wk)	>3 days	Next planned weekly dosing date
3 to 6	Every 2 weeks (q2wks)	>7 days	Next planned every 2 weeks dosing date
7+	Every 4 weeks (q4wks)	>14 days	Next planned every 4 weeks dosing date

Any dose withholding of more than 28 days due to toxicity will result in permanent discontinuation of daratumumab. Dose withholdings of more than 28 days for other reasons should be discussed with the Sponsor. If a dose delay occurs, then pharmacokinetic and pharmacodynamic assessments should be performed on the actual day of study drug administration, not on the original scheduled administration day.

A study drug dose withheld for more than 3 days from the per-protocol administration date for any reason other than toxicities suspected to be related to daratumumab should be brought to the attention of the Sponsor at the earliest possible time. Subjects missing ≥ 3 consecutive planned doses of study drug for reasons other than toxicity should be withdrawn from treatment, unless, upon consultation with the Sponsor and the review of safety and efficacy, continuation is agreed upon.

➤ Pomalidomide

Doses of pomalidomide may be modified/interrupted following hematologic adverse reactions (neutropenia or thrombocytopenia) and for other Grade 3 or 4 adverse reactions judged to be related to the drug.

Pomalidomide interruption or discontinuation should be considered for Grade 2-3 skin rash. Pomalidomide must be discontinued for angioedema, Grade 4 rash, exfoliative or bullous rash and for Stevens-Johnson syndrome/toxic epidermal necrolysis related to pomalidomide, and should not be resumed following discontinuation for these reactions.

Interstitial lung disease (ILD) and related events, including cases of pneumonitis, have been observed with pomalidomide. Careful assessment of subjects with an acute onset or unexplained worsening of pulmonary symptoms should be performed to exclude ILD. Pomalidomide should be interrupted pending investigation of these symptoms and if ILD is confirmed, appropriate treatment should be initiated. Pomalidomide should only be resumed after a thorough evaluation of the benefits and the risks.

Based on the pomalidomide SmPC, subjects should be advised to report febrile episodes promptly. Physicians should observe subjects for signs of bleeding including epistaxis, especially with use of concomitant medicinal products known to increase the risk of bleeding. Complete blood counts should be monitored at baseline, weekly for the first 8 weeks and monthly thereafter. A dose modification may be required. Patients may require use of blood product support and/or growth factors.

If strong inhibitors of CYP1A2 (ie., ciprofloxacin, enoxacin, and fluvoxamine) are co-administered with pomalidomide, reduce the dose of pomalidomide by 50%.

Instructions for dose interruptions and reductions for pomalidomide related to hematological adverse reactions are outlined in the table below:

Toxicity	Dose Modification

• Neutropenia
○ ANC* $<0.5 \times 10^9/L$ or febrile neutropenia (fever $\geq 38.5^\circ C$ and ANC $<1 \times 10^9/L$)○ ANC return to $\geq 1 \times 10^9/L$○ For each subsequent drop $<0.5 \times 10^9/L$○ ANC return to $\geq 1 \times 10^9/L$	Interrupt pomalidomide treatment, follow CBC** weekly. Resume pomalidomide at 3 mg daily Interrupt pomalidomide treatment Resume pomalidomide treatment at 1 mg less than the previous dose.

• Thrombocytopenia
○ Platelet count $<25 \times 10^9/L$○ Platelet count return to $\geq 50 \times 10^9/L$○ For each subsequent drop $<25 \times 10^9/L$○ Platelet count return to $\geq 50 \times 10^9/L$	Interrupt pomalidomide treatment, follow CBC** weekly Resume pomalidomide treatment at 3 mg daily Interrupt pomalidomide treatment Resume pomalidomide treatment at 1 mg less than the previous dose

* ANC – Absolute Neutrophil Count, ** CBC Complete Blood Count

To initiate a new cycle of pomalidomide, neutrophil count must be $\geq 1 \times 10^9/L$ and the platelet count $\geq 50 \times 10^9/L$.

In case of neutropenia, the physician should consider the use of growth factors.

For other Grade 3 or 4 adverse reactions judged to be related to pomalidomide, stop treatment and restart treatment at 1 mg less than the previous dose when an adverse reaction has resolved to \leq Grade 2 at the physician's discretion. If adverse reactions occur after dose reductions to 1 mg, then the medicinal product should be discontinued.

Investigators should follow the local label of pomalidomide for the management of interactions with other medical products.

➤ Dexamethasone

Instructions for dose modifications of dexamethasone are shown in the table below. Refer to this table for recommended dose reductions, and to the dexamethasone package insert, which states that dosage requirements are variable and must be individualized. Note that this table represents suggested dose modifications of dexamethasone, but physician discretion and clinical judgment should prevail.

Dyspepsia = Grade 1-2	Maintain dose and treat with histamine (H2) blockers or equivalent. Decrease by one dose level if symptoms persist.
Dyspepsia \geq 3	Interrupt dose until symptoms are controlled. Add H2 blocker or equivalent and decrease one dose level when dose restarted.
Edema \geq Grade 3	Use diuretics as needed and decrease dose by one dose level.
Confusion or mood alteration \geq Grade 2	Interrupt dose until symptoms resolve. When dose restarted decrease dose by one dose level.
Muscle weakness \geq Grade 2	Interrupt dose until muscle weakness \leq Grade 1. Restart with dose decreased by one level.
Hyperglycemia \geq Grade 3	Decrease dose by one dose level. Treat with insulin or oral hypoglycemic agents as needed
Acute pancreatitis	Discontinue subject from dexamethasone treatment regimen.
Other \geq Grade 3 dexamethasone-related adverse events	Stop dexamethasone dosing until adverse event resolves to \leq Grade 2. Resume with dose reduced by one level.

Dexamethasone dose reduction levels:

Dose reduction levels (<75 years of age): Starting dose 40 mg; dose level -1 20 mg; dose level-2 10 mg on Days 1, 8, 15 and 22 of each 28-day treatment cycle.

Dose reduction levels (≥ 75 years of age): Starting dose 20 mg; dose level -1 12 mg; dose level-2 8 mg on Days 1, 8, 15 and 22 of each 28-day treatment cycle.

If recovery from toxicities is prolonged beyond 14 days, then the dose of dexamethasone will be decreased by one dose level.

Investigators should follow the local label of dexamethasone for the management of interactions with other medical products.

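### Pomalidomide cytopenia table: the fixed 3 mg restart after a first neutropenia or thrombocytopenia has no condition on the current dose, so a subject already at 3 mg gets no reduction

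*Combined protocol and SAP*

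**What the plan says.** Section 6.1.5 introduces the pomalidomide table as follows: "Instructions for dose interruptions and reductions for pomalidomide related to hematological adverse reactions are outlined in the table below". The first neutropenia row is triggered by ANC <0.5 x 10^9/L "or febrile neutropenia (fever" with ANC <1 x 10^9/L). Once ANC is back to at least 1 x 10^9/L, the instruction is "Resume pomalidomide at 3 mg daily". The first thrombocytopenia row is triggered by platelets <25 x 10^9/L. After recovery to at least 50 x 10^9/L it reads "Resume pomalidomide treatment at 3 mg daily".

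For each later drop in the same cell line, both parts of the table use a relative step: "Resume pomalidomide treatment at 1 mg less than the previous dose". Below the table, a further rule opens "For other Grade 3 or 4 adverse reactions judged to be related to pomalidomide" and continues "stop treatment and restart treatment at 1 mg less than the previous dose", once the reaction has resolved to Grade 2 or less, at the physician's discretion. It adds that the drug should be discontinued if reactions occur after reduction to 1 mg.

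Section 6.1.4 gives the starting dose as 4 mg once daily on Days 1 to 21 of a 28-day cycle.

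**The concern.** A subject can be below 4 mg when the first event in a cell line occurs. The two cytopenias have separate rows, and the rule for other related Grade 3 or 4 reactions also lowers the dose. For such a subject the figure printed in the first-event row is not a reduction, although the table is introduced as giving reductions.

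At stake is the restart dose after severe neutropenia, febrile neutropenia or severe thrombocytopenia. A site that restarts a 3 mg subject at 3 mg is following the table exactly, so nothing prompts it to look again. A site that goes to 2 mg departs from the printed number, and no other protocol text supplies a different one.

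**Working it through.** There is no statistical figure to reproduce. The check applies the section 6.1.5 rules literally from the 4 mg start.

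**Step 1: the five restart rules side by side.**

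| Trigger | Restart dose | Depends on current dose? |
|---|---|---|
| First neutropenia | 3 mg | No |
| First thrombocytopenia | 3 mg | No |
| Repeat neutropenia, ANC <0.5 | previous - 1 mg | Yes |
| Repeat thrombocytopenia, platelets <25 | previous - 1 mg | Yes |
| Other related Grade 3 or 4 reaction | previous - 1 mg | Yes |

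**Step 2: effect of a first-event row by current dose.** Change = (restart - current) / current. Total per dosing period = daily dose x 21 days.

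| Current dose | Restart as printed | Total per 21 dosing days | Change | Restart with a 1 mg step |
|---|---|---|---|---|
| 4 mg | 3 mg | 84 to 63 mg | (3-4)/4 = -25% | 3 mg (-25%) |
| 3 mg | 3 mg | 63 to 63 mg | (3-3)/3 = 0% | 2 mg (-33%) |
| 2 mg | 3 mg | 42 to 63 mg | (3-2)/2 = +50% | 1 mg (-50%) |

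**Step 3: which sequences reach these cases.** Let N = ANC <0.5, P = platelets <25 and G = another related Grade 3 or 4 reaction. Febrile neutropenia is left out because its repeat rule can be read in more than one way (Step 5).

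- Two events, 3 x 3 = 9 orders. Four contain a restart with no reduction: NP, PN, GN and GP, each 4-3-3. The other five go 4-3-2. None raises the dose, because 2 mg is not reached before a third event.
- Three events, 3 x 3 x 3 = 27 orders. Twelve contain a restart with no reduction: NPN, NPP, NPG, PNN, PNP, PNG, GNN, GNG, GPP and GPG (4-3-3-2), and GNP and GPN (4-3-3-3). Six others raise the dose: NNP, NGP, PPN, PGN, GGN and GGP (4-3-2-3). The remaining 27 - 12 - 6 = 9 go 4-3-2-1.
- With a 1 mg step in the first-event rows, every two-event order goes 4-3-2 and every three-event order goes 4-3-2-1, so all of these counts become 0.

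The enumeration treats each G as an automatic 1 mg reduction, although that rule leaves room for discretion. Dropping G and keeping only the two cytopenias leaves the pattern in place. Of the 4 two-event orders, 2 have no second reduction (NP, PN). Of the 8 three-event orders, 4 contain a restart with no reduction (NPN, NPP, PNN, PNP) and 2 raise the dose (NNP, PPN). These are counts of orders, not probabilities.

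**Step 4: does other text supply the level?** Section 5.3.1 says when treatment must stop. The daratumumab dose-delay text in 6.1.5 says when study treatment is withheld and resumed. Section 6.1.4 and the opening of the pomalidomide text in 6.1.5 say that dosing may be modified. None gives a restart dose for a subject already reduced. The statement "physician discretion and clinical judgment should prevail" belongs to the dexamethasone table. Section 6.1.4 also points to the SmPC, which is not among the documents.

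**Step 5: repeat febrile neutropenia at ANC 0.5 to <1.0.** The dose-delay text in 6.1.5 already requires study treatment to be withheld for febrile neutropenia, whatever its relationship to the drug. A new pomalidomide cycle also needs ANC of at least 1 x 10^9/L. Only the restart level is open. For a subject at 3 mg it is 3 mg if the first row is applied again, no stated level if no row applies, or 3 - 1 = 2 mg under the rule for other reactions.

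**The case against.** The strongest case on the other side is that the table is adequate in use.

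- *Safeguards around the 3 to 3 mg case.* The drug is interrupted, blood counts are followed weekly, restart waits for recovery, growth factors are to be considered for neutropenia, and a later drop in the same cell line steps down 1 mg. The documents do not show that a first event in a second cell line must force a second reduction. This stands as far as it goes: 3 to 3 mg is not shown to be unsafe. But a table of reductions that yields none, beside three rules that always step down, is still a defect in the rule as written.
- *Clinical judgement.* Sections 6.1.4 and 6.1.5 allow doses to be modified on clinical and laboratory findings, and the SmPC may settle the matter. Judgement would probably prevent an actual increase. It does not supply a number, and the SmPC cannot be checked here.
- *Late reach.* Appendix 12 confines remaining treatment to continued access, up to 30 September 2024, on the established regimen. Section 2.3.1 says that pomalidomide reactions tend to come in the first 2 cycles. Both points stand and limit the benefit of an edit now.

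A reader might go further and infer that the table sends subjects back to a higher dose as a practical hazard. The documents do not support that. The 2 to 3 mg case needs three qualifying events in particular orders, contradicts the table's own introduction, and few clinicians would follow it. A reader might also infer that repeat febrile neutropenia is left unmanaged. It is not: withholding is already required, and a mandatory step-down there would be a clinical preference that the text does not show the authors intended.

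**Conclusion.** The concern holds as a minor patient-safety correction to a stated dosing rule. Both first-event rows lack a condition on the current dose. Read literally, they give no reduction from 3 mg, which is the main case, and a rise from 2 mg, which is rare. The literal reading and the 4 mg start are the only assumptions behind those two results. The sequence counts also assume that every other related Grade 3 or 4 reaction leads to a 1 mg cut.

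The size in subjects is unknown. Sections 2.2 and 2.3.1 report Grade 3 or 4 neutropenia and thrombocytopenia of 48% and 22% with pomalidomide plus low-dose dexamethasone, and 77% and 19% with daratumumab added. These show that both cell lines are affected often enough for the main case to be plausible. They are not estimates of subjects affected, because the table's triggers are stricter than Grade 3 and the joint frequency is not given.

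The rule applies to both arms. No efficacy result, alpha or power figure changes, and nothing here supports a claim about the treatment comparison.

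**What to change.** Change both first-event rows to: *Resume at 3 mg daily if the previous dose was 4 mg; if the dose was already reduced for toxicity, resume at 1 mg less than the previous dose; if already at 1 mg, discontinue; never resume above the previous dose.* This leaves 4 to 3 mg as it is and matches the 1 mg step in the other three rules. The 1 mg clause follows the discontinuation rule already in section 6.1.5.

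State separately how the rows apply to a subject whose dose was halved for a strong CYP1A2 inhibitor (4 x 0.5 = 2 mg), since that is not a toxicity reduction.

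Optionally, state the restart level for repeat febrile neutropenia at ANC 0.5 to <1.0. That choice is clinical.

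The edit is to two table rows plus one added sentence, with no extra visits, data or subjects. It is nevertheless a protocol amendment: section 13.2 requires IRB/IEC and/or CA approval before a change is implemented, and sites would need to be told. It would now reach only subjects still on treatment.

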6.1.4 Dosing and Administration

Table 6.1 shows dosing and administration of daratumumab, pomalidomide and dexamethasone. See section below for details.

Table 6.1: Dosing and Administration

1. On days when daratumumab is administered, dexamethasone will be administered to subjects in DPd arm in the clinic and will serve as the treatment dose of steroid as well as the required pre-medication prior to daratumumab infusion. Note 20 mg PO weekly for subjects ≥ 75 years of age.

➤ Daratumumab

Daratumumab will be given at a dose of 16 mg/kg administered as an IV infusion (Dara IV) or 1800 mg subcutaneously (Dara SC) at weekly intervals (QW) for 8 weeks, then every 2 weeks (Q2W) for an additional 16 weeks, then every 4 weeks (Q4W) thereafter. See *Section 6.1.5* for guidelines for the IV/SC infusion of daratumumab and *Section 7.3.1* for pre-infusion medications and *Section 7.3.2* for post-infusion medications to be given to mitigate potential IRRs and the management of these reactions.

Subjects should be monitored throughout the infusion and the post-infusion period.

See the SmPC for more details about daratumumab.

➤ Pomalidomide

The recommended starting dose of pomalidomide is 4 mg once daily taken orally on Days 1 to 21 of repeated 28-day cycles. Dosing is continued or modified based upon clinical and laboratory findings. Pomalidomide should be taken at the same time each day. The capsules should not be opened, broken, or chewed. This medicinal product should be swallowed whole, preferably with water, with or without food. If the subject forgets to take a dose of pomalidomide on one day, then the subject should take the normal prescribed dose as scheduled on the next day. Subjects should not adjust the dose to make up for a missing dose on previous days.

See the SmPC for more details about pomalidomide.

➤ Dexamethasone

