The recommended dose of dexamethasone is 40 mg (20 mg for patients ≥ 75 years of age) orally, once daily on Days 1, 8, 15, and 22 of each 28-day treatment cycle. During the weeks when the subject receives daratumumab, half of the dexamethasone dose (20 mg) will be administered on the day of infusion as the pre-infusion medication (IV preferred, see [Section 7.3.1](#)) and the remaining dose (20 mg PO) will be self-administered by the subject the following day. This applies only for subjects who are taking the full 40 mg dexamethasone dose. The subjects who are taking 20 mg of dexamethasone (≥ 75 years of age) will receive the entire 20 mg dose as a pre-infusion medication on the day of daratumumab infusion.

See the SmPC for more details about dexamethasone.

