7.3.1 Pre-infusion Medication

Pre-infusion medications for all subjects receiving daratumumab will be administered as described in the Schedule of Events ([Table 7.3](#)). On daratumumab infusion days, subjects will receive the following medications approximately 1 hour prior to daratumumab infusion:

- Dexamethasone 20 mg IV (preferred) or PO (an equivalent of long-acting corticosteroid may substitute [[Appendix 8](#)]);
- Paracetamol (acetaminophen) 650 to 1000 mg IV or PO; and
- An antihistamine (diphenhydramine 25 to 50 mg IV or PO, or equivalent, but avoid IV use of promethazine) ([Appendix 7](#)).
- Leukotriene inhibitor (optional) on C1D1: montelukast 10 mg PO.

If necessary, oral pre-infusion medications may be administered outside of the clinic on the day of the infusion, provided they are taken within 1 to 3 hours prior to the infusion.

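### The fixed 20 mg dexamethasone dose before daratumumab conflicts with the 10, 12 and 8 mg reduction levels, so on the literal text those reductions cannot be applied on daratumumab days in the DaraPomDex arm

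*Combined protocol and SAP*

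**What the plan says.** Four places in the protocol bear on the dexamethasone dose on a daratumumab day.

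- **Section 7.3.1** is mandatory in wording: "On daratumumab infusion days, subjects will receive the following medications approximately 1 hour prior to daratumumab infusion". The first item listed is "Dexamethasone 20 mg IV (preferred) or PO (an equivalent of long-acting corticosteroid may substitute", with a pointer to the conversion table in Appendix 8. No exception is made for a subject whose dexamethasone has been reduced.
- **Table 6.1, footnote 1 (Section 6.1.4)** says that in the DaraPomDex arm the in-clinic dose "will serve as the treatment dose of steroid as well as the required pre-medication prior to daratumumab infusion".
- **Section 6.1.4, Dexamethasone** splits a 40 mg dose into 20 mg before daratumumab and 20 mg the next day, and limits the split: "This applies only for subjects who are taking the full 40 mg dexamethasone dose". Subjects aged 75 or over on 20 mg "will receive the entire 20 mg dose as a pre-infusion medication on the day of daratumumab infusion". Doses below 20 mg are not mentioned.
- **Section 6.1.5, Dexamethasone** gives the reduction levels. Under 75 years: "Starting dose 40 mg; dose level -1 20 mg; dose level-2 10 mg on Days 1, 8, 15 and 22". At 75 or over, from a start of 20 mg: "dose level -1 12 mg; dose level-2 8 mg on Days 1, 8, 15 and 22". The accompanying toxicity table is described as suggested and subject to clinical judgement. A one-level decrease is nevertheless worded as required when recovery takes more than 14 days.

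**The concern.** The footnote to Table 6.1 closes the easiest way out, which would be to treat the pre-infusion steroid as separate from the treatment dose. One administration is both. For a subject at 10, 12 or 8 mg, Section 7.3.1 therefore calls for 20 mg on a day when Section 6.1.5 calls for less.

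A subject reduced because of steroid toxicity could thus receive more steroid than the reduced level specifies. Sites that resolve the conflict differently would also treat similar subjects differently. PomDex subjects have no pre-infusion dose, so the conflict exists in one arm only and could affect the comparison of steroid-related toxicity between arms.

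**Working it through.** The plan states no figure of its own here, so the check is one of consistency followed by dose arithmetic.

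**Inputs**

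- Dexamethasone days per 28-day cycle: 4 (Days 1, 8, 15 and 22; Sections 6.1.4 and 6.1.5).
- Daratumumab days per cycle, *d*: 4 in Cycles 1-2, 2 in Cycles 3-6 and 1 from Cycle 7 (Section 6.1.4 and Table 7.3). Each is also a dexamethasone day.
- Reduced level, *L*: 20 or 10 mg under 75 years; 12 or 8 mg at 75 or over (Section 6.1.5).
- Pre-infusion dose: 20 mg (Section 7.3.1).

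**Formulas**

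- Scheduled per cycle at the reduced level = 4 × *L*.
- Per cycle if 20 mg is kept on daratumumab days = *d* × max(20, *L*) + (4 − *d*) × *L*.

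Example, *L* = 10 mg in Cycles 3-6: 2 × 20 + 2 × 10 = 60 mg, against 4 × 10 = 40 mg.

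| Level | Scheduled per cycle | Cycles 1-2 | Cycles 3-6 | Cycle 7 onward |
|---|---|---|---|---|
| 20 mg (<75, level -1) | 80 mg | 80 mg (0%) | 80 mg (0%) | 80 mg (0%) |
| 10 mg (<75, level -2) | 40 mg | 80 mg (+100%) | 60 mg (+50%) | 50 mg (+25%) |
| 12 mg (≥75, level -1) | 48 mg | 80 mg (+67%) | 64 mg (+33%) | 56 mg (+17%) |
| 8 mg (≥75, level -2) | 32 mg | 80 mg (+150%) | 56 mg (+75%) | 44 mg (+38%) |

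**Reading the table**

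- In Cycles 1-2 every dexamethasone day is a daratumumab day, so the three lower levels change nothing.
- From Cycle 3 they take partial effect, because the days without daratumumab can follow the reduced level.
- The first reduction under 75 years, 40 to 20 mg, raises no conflict. At 75 or over, even the first reduction, 20 to 12 mg, does.

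**Related gap.** Section 6.1.5 stops dexamethasone for acute pancreatitis, and Section 5.3.1 allows daratumumab to continue after dexamethasone is discontinued. Section 7.3.1 does not say what then happens to the pre-infusion steroid.

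**The case against.** The strongest reply is physician discretion. Section 6.1.5 says the dexamethasone reductions are suggestions, and Section 4.1 gives dexamethasone by standard practice at a recommended dose. If the pre-infusion dose is the treatment dose, discretion over one arguably reaches the other. This has some force: a site could reasonably act on it. But the discretion is attached to the reduction table, while Section 7.3.1 is worded as a requirement. Where the protocol wants flexibility in these medications it says so: the leukotriene inhibitor is optional, and post-infusion medication may be waived after four doses. It says nothing similar about the 20 mg. If discretion does apply, practice may vary by site, which is also a reason to state the rule.

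Three limits on the point stand:

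- The reductions are fully cancelled only in Cycles 1-2. From Cycle 7 the excess is 8 to 12 mg per cycle.
- Only the footnote of Table 6.1 appears in the text available for review, so the body of the table could not be checked for a rule on reduced doses.
- The primary PFS cut-off was 21 July 2020 (Table 7.3), so new wording cannot change data already collected for that analysis.

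A reader might also infer that the dexamethasone backbone differs enough between arms to cloud attribution of the PFS effect to daratumumab. The documents do not support that. They give no frequency of reductions below 20 mg, so the number of subjects affected cannot be bounded, and required pre-medication is part of the regimen being compared. Nor is a separate dose-intensity analysis needed. Section 10.4.6 already summarises cumulative dose and dose intensity for each component of study treatment, by arm and by cycle, and the Table 6.1 footnote makes the pre-infusion dose part of that treatment.

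**Conclusion.** The contradiction is real on the visible text. At 10, 12 and 8 mg, Sections 6.1.5 and 7.3.1 cannot both be followed on a daratumumab day, and Section 6.1.4 does not settle which governs. It arises only in the DaraPomDex arm.

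If 20 mg is kept, the excess over the reduced level is 32 to 48 mg per cycle in Cycles 1-2, 16 to 24 mg in Cycles 3-6 and 8 to 12 mg from Cycle 7. These figures assume daratumumab on schedule, all four dexamethasone doses given, and a literal reading of Section 7.3.1. They apply only to subjects at those three levels, whose number is not given.

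The consequence is for steroid exposure after toxicity and for comparing steroid-related safety between arms. No effect on PFS, sample size, power or alpha is shown.

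**What to change.** Reconcile Sections 6.1.4, 6.1.5 and 7.3.1 and Table 6.1 so that they give one consistent rule for dexamethasone on daratumumab days after a reduction below 20 mg, and make clear how far physician discretion extends to the pre-infusion dose. The same text could close the gap for subjects who continue daratumumab after stopping dexamethasone. What the rule should be is a clinical decision for the sponsor.

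The cost is protocol wording only, with no new data collection or analysis. It remains relevant after the primary analysis because Appendix 12 refers dosing in the extension phase back to Section 6.1.4.
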